## 1.0 STUDY PROTOCOL

### 1.1 Research abstract

Estimation of breast cancer risk is important since it enables selection of a high and moderate risk population who benefit from more frequent breast screening and the introduction of targeted measures to reduce risk such as lifestyle change, chemoprevention and risk reducing surgery. Traditionally, risk is estimated by combining information concerning family history and non-familial factors, such as age of menarche and first pregnancy. Subsequent management is related to the degree of risk (high, moderate or average) according to NICE guidelines. Members of the research team and others have added mammographic density (MD) and breast cancer risk associated single nucleotide polymorphisms (SNPs) to risk models which improves the accuracy of risk estimation but which may change the original given risk and risk management given before the updated models became available. The objective of this study is to quantify change in risk and risk management when MD and SNPs are incorporated into two standard models (Tyrer-Cuzick v8 & BOADACEA V). A second objective of the study is to determine the psychological effects of change of risk and management. This study will use participant data from the Family History Risk (FH-Risk) study to recalculate risk. The FH-Risk study population consists of 954 women referred to the Family History Risk and Prevention Clinic (FHRPC) between 2000 and 2012 who gave informed consent for DNA testing and estimation of MD as part of the FH-Risk study which recruited between 2010 and 2012. Change in risk and management will be calculated by comparing given risk at the time of clinic entry compared with re-estimated risk when MD and SNPs are added to the risk models according to NICE guidelines. Risk will be estimated retrospectively at the time of entry to the clinic and the time of latest follow up. All of those who took part in the FH-Risk study will be given the opportunity to discuss their updated risk.

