**Table 1. Nice categories of lifetime BC risk and subsequent management dependant on risk**

	Moderate risk (17-29%)	High risk (>30%)
Yearly screening	up to age 50	up to age 60
Chemoprevention	'consider'	'offer'
Risk reducing surgery	none	offer

\*Many referrals will be assessed at 'average' risk and returned to primary care

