**Figure 3. BIRADS categories (see <https://densitas.health/blog/breast-density-scales>)**

## 2. DNA measurements of risk of breast cancer

Genome wide association studies (GWAS) (Michailidou 2017, Turnbull 2010, Easton 2007, Mavaddat 2019) reported a series of common genetic variants (SNPs) each carried by 28-44% of the population associated with a 1.07-1.26 relative risk of BC. The first seven breast cancer risk associated variants were published in 2007 (Easton 2007). At the time of the initiation of the FH-Risk study (see below for explanation of FH-Risk study) in 2010, details of 18 variants were available. As a result of studies from the Breast Cancer Associated Consortium (which includes data from Manchester) a total of 313 variants are available and can be incorporated into the Tyrer-Cuzick v8 and BOADICEA V models (Mavaddat 2019). In an early report from the FH-Risk study we demonstrated that adding the results

[figure not shown]
of the 18 SNP score to the Tyrer-Cuzick model altered risk such that 25% of women increased risk and 25% decreased risk indicating the importance of SNPs in defining risk in women at moderate and high risk of breast cancer (Evans 2017).

PVs (mutations) in the TP53, BRCA1 and BRCA2 genes were shown to be associated with a high risk breast cancer in the 1990ies (Malkin 1990, Miki 1994, Wooster 1995). Since a number of potential breast cancer genes have been discovered. In order to delineate genes which are definitively related to breast cancer the Breast Cancer Association Consortium estimated the breast cancer risk association of 34 potentially important genes in 67,269 women diagnosed with breast cancer and 59,299 controls from a large number of study groups including PROCAS and FH-Risk studies from Manchester (Dorling 2020). The genes reported with PVs which were associate with a greater than twofold increase in breast cancer risk are *ATM*, *BRCA1*, *BRCA2*, *CHEK2*, *PALB2*, *BARD1*, *RAD51C*, *RAD51D* and *TP53*. **All women in the FH-Risk study have been tested for SNP313 and all potential breast cancer genes.**

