#### **Family History Risk study (FH-Risk)**

The FH-Risk study aimed to assess, validate and improve breast cancer risk assessment models from the FHRPC at the Nightingale Centre in the North West of England (Evans et al., 2016). The FH-Risk study (funded by NIHR) recruited 954 women without a breast cancer diagnosis between November 2010 and November 2012 in a nested case control study who were age-matched to women who had been diagnosed with breast cancer (Evans 2017). The women in the control group, who form the basis of the study outlined in this protocol, had their first FHRPC visit between ~2000 and 2012. At their first visit if during the period 1993-2010, risk was assessed using Claus tables modified by hormonal risk factors as this is more accurate for predicting risk compared with family history alone (Amir 2003, Evans 2013). Later in this period, the TC V6 model (Tyrer, Duffy, & Cuzick, 2004) was validated to be the most accurate available model to predict individual breast cancer risk and was therefore subsequently used in the FHRP. Women received individual lifetime risk estimates and counselling when attending the FHRPC for the first time. Those with lifetime risks of 1 in 4-6 (moderate risk) or >1 in 3 (high risk) were included in the clinic annual screening programme according to NICE Guidelines. The women also provided blood samples to assess SNPs and other genetic information between 2010-2012. They received the results related to SNP risk via letter (as the SNPs had not been fully validated at time of sending letters this simply indicated whether risk had not changed substantially with odds ratios of 0.5-2 or if below or above that risk had decreased or increased as a result of the DNA tests. No personalized feedback was given). The results of estimated MD were not fed back at the time. The research group were later able to validate that the use of 18 SNPs accurately moved 50% of women a whole risk category upwards or downwards (Evans et al., 2017).

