### **3.0 STUDY DESIGN & PROTOCOL**

#### **3.1: Part 1: Re-evaluation of breast cancer risk in the FH-Risk study population.**

##### **Participants in the FH-Risk study**

A total of 954 women were entered into the NIHR FH-Risk study which was designed to assess how standard breast cancer risk estimates based on familial and non-familial factors (components of the standard Tyrer-Cuzick risk model) might be altered by the addition of MD and the newly discovered (at the time) breast cancer SNPs. Women under follow up in the Manchester FHRPC were recruited between November 2010 and November 2012 to the FH-Risk study. Recruitment was from women who may have previously been referred (from approximately 2000 onward) or women newly referred to the clinic during the recruitment period between 2010 and 2012.

Feedback of the results of how SNP18 affected risk was given in 2013. The risk change was given in general terms since the precise importance of the risk change was only partially clear and the algorithm was not yet fully validated. Feedback on MD was not given as previously suggested because analysis was not possible to compare with cancers at the time as the raw mammogram images required for processing MD were not retained. In 2017 v8 of the Tyrer-Cuzick model and in 2019 v5 of the BOADICEA model (CanRisk) was introduced which incorporated density measures and the assessment of SNPs.

All women in the FH-Risk study were/are undergoing annual mammography. They were/are discharged to the NHSBSP at age 50 if moderate risk or at age 60 if high risk as per NICE clinical

guidelines. At present (October 2020) approx. 271 patients remain under annual follow up for mammography and should be given the opportunity to learn of their revised risk estimate, as this information could change their entitlement to risk reducing strategies. Women who have been discharged will also be given the opportunity to be informed on their updated breast cancer risk estimate.

All FH-Risk women had blood taken for genetic studies. A copy of the consent form and the participant information sheet for FH-Risk is given in appendix 1. The following statements on the consent form are of high importance since women indicated:

1. *I consent to the storage of my DNA sample for future research.*
2. *I consent to the gifting of my blood sample for future research.*
3. *I agree to my existing mammograms and information from my Family History questionnaire(s) being used in this research.*

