## 3. Analysis

The primary analysis will compare the risk categories and risk scores for the risk prediction models for women at entry to the clinic (or age 40) and at last follow-up in the clinic, and will compare the risk scores given by TCv8 and BOADICEA using different model inputs.

- i) **Change in risk categories** – NICE risk categories (average, moderate and high) will be compared by creating cross tabulations of risk categories at entry and at last follow-up – the number (and percentage) of women moving up and down risk categories will be

reported and the McNemar-Bowker test will be used to determine whether the change in risk categories is statistically significant between the two time points.

- ii) **Change in 10-year and lifetime risk scores** - change in continuous risk measures (10-year and lifetime risk estimates) will be estimated from TCv8 and BOADICEA risk prediction models. Normality and skewness of 10-year and lifetime breast cancer risk scores will be assessed. Where there is evidence of non-normality scores will be transformed. Scatterplots and correlation coefficients will be used to examine the relationship between 10-year and lifetime risk estimates at baseline and at latest follow-up.

Descriptive statistics will be used to report change in risk scores from time at entry to latest follow-up and will be compared using a paired t-test. Linear regression will be used to determine which risk factors (e.g. SNP313, MD) are associated with change in risk score.

- iii) **Comparison between risk models** - descriptive statistics will be used to report risk scores from TCv8 and the BOADICEA models and differences in risk scores compared. Models will be compared using a) classical risk factors alone, b) classical risk factors plus mammographic density, as measured by BIRADS, which can be included in both models and c) classical risk factors plus mammographic density and SNPs. Scatterplots and correlation coefficients will be used to examine the relationships between models and Bland-Altman plots used to show the agreement between the models.

Secondary analysis will focus on the comparison between differences in mammographic density measures and the relationship with risk scores using TCv8.

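### The McNemar-Bowker test of entry versus last-follow-up NICE category tests net direction between two time points, so it cannot show whether adding the new risk factors changes category

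*Combined protocol and SAP*

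**What the plan says.** Item i of 3. Analysis cross-tabulates NICE category (average, moderate, high) at entry against category at last follow-up, counts the women who go up and down, and adds that "the McNemar-Bowker test will be used to determine whether the change in risk categories is statistically significant" from entry to last follow-up. No other test is applied to categories for the primary objectives. The first of those (SAP, 1. Objectives) is the change in category caused by adding new factors to the standard models. The second is how far the new models alter the risk that women had been told.

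The entry category is described in two ways. The research abstract (1.1) says: "Change in risk and management will be calculated by comparing given risk at the time of clinic entry compared with re-estimated risk". The same abstract also has risk worked out retrospectively as at clinic entry, and the SAP's primary endpoints are categories from TCv8 and BOADICEA v5.

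On who is in the cohort, section 1.2 (FH-Risk study) says: "Those with lifetime risks of 1 in 4-6 (moderate risk) or >1 in 3 (high risk) were included in the clinic annual screening programme". The footnote to Table 1 says that referrals assessed at average risk are "returned to primary care". Section 3.1 says: "All women in the FH-Risk study were/are undergoing annual mammography". On the size of earlier changes, section 1.2 reports that with the 18-SNP score "25% of women increased risk and 25% decreased risk".

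**The concern.** The test's null hypothesis is symmetry: as many women move from category i to j as from j to i, for each pair. Three things separate that null from the question asked.

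- **Direction, not amount.** Many women can be reclassified while the pairs stay balanced.
- **Mixed causes.** Between entry and last follow-up, age and questionnaire data change as well as the model inputs. If the entry value is the risk given at the time, the model changes too. Section 3.1 says that V8 runs to age 85, where V6 ran to 73 or 80, and that it gives somewhat higher risks in any case.
- **Selection.** Women joined the programme on a moderate or high given risk. If that given risk supplies the rows of the table, there is essentially nobody in the average row to move up.

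The abstract expects the results to inform the next NICE guideline. A p-value from this table could be credited to density, SNPs or gene results when it reflects selection or elapsed time. A non-significant one could be taken as stability when many women have moved.

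**Working it through.** **Inputs from the documents.** N = 954 for recalculation (section 3.1). The analysis set is women with two risk appointments (2. Methods), and its size is not given. The clinic split is 49.7% high and 50.3% moderate (section 1.2). Cut-points are 17% and 30% lifetime risk (Table 1). No alpha is stated for Part 1; 0.05 is assumed.

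**1. The plan's own figures.** Pilot: 53/106 = 50.0% down, 40/106 = 37.7% unchanged, 13/106 = 12.3% up. These reproduce. Collapsed to up versus down, McNemar gives (53 − 13)²/(53 + 13) = 1600/66 = 24.2 on 1 df, p = 8.5 × 10⁻⁷. A downward excess is also what selection on high entry risk would produce, so the p-value does not separate the two explanations.

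**2. The statistic.** X² = Σ (nij − nji)²/(nij + nji) over the three pairs, 3 df, 5% critical value 7.815.

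**3. Given risk as the entry category.** With an empty average row, m moves from moderate to average contribute (m − 0)²/(m + 0) = m. If the other pairs balance:
- m = 7: X² = 7.0, p = 0.072
- m = 8 (8/954 = 0.8%): X² = 8.0, p = 0.046
- m = 6, if the empty average/high pair is dropped (2 df): p = 0.0498

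**4. Same amount of change, opposite answers.** Suppose 238 women move up and 238 down (about 25% of 954 each way). With an empty average row and no high-to-average moves, every upward move is moderate to high. Let a of the downward moves be moderate to average. Then X² = a + a²/(476 − a).
- a = 0: X² = 0, p = 1
- a = 8: X² = 8 + 64/468 = 8.14, above 7.815

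Half the cohort is reclassified in both cases. The documents do not say how the SNP18 moves split between pairs, so this is an illustration.

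**5. Simulation with no systematic change.** Log lifetime risk is normal with the same mean and SD at both readings, and the mean is set so that 49.7% of selected women are high. The SD of log risk (0.3, 0.4, 0.5) and the correlations are assumptions. n = 954, 400 replicates.

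| Correlation between readings | Selected on entry risk | Not selected |
|---|---|---|
| 0.6 | 100% | 3.3-5.8% |
| 0.8 | 100% | not run |
| 0.9 | 94-100% | 1.0-2.8% |
| 0.95 | 75.5-100% | not run |
| 0.99 | 15-99.8% | not run |
| about 1 (no reclassification) | 0% | not run |

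At SD 0.3 and correlation 0.9, the average moderate-to-average count is 12.6 against 0 with selection, contributing 12.6. Without selection it is 12.4 against 12.2, contributing (0.2)²/24.6 = 0.002.

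With 271 women (the number still in follow-up, used only as a smaller n) and correlation 0.8, rejection is 21%, 95% and 100% at SD 0.3, 0.4 and 0.5.

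**6. Recalculated risk as the entry category.** Selection acts on given risk, and the test compares two recalculated categories.
- Both equally correlated with given risk (0.7 and 0.7): rejection 1.5-4.3%
- Entry estimate more correlated with given risk than the update (0.8/0.6, 0.9/0.7 or 0.9/0.8): rejection 7.5-97%

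**The case against.** The strongest reply is that the SAP names TCv8 and BOADICEA categories as endpoints and feeds baseline questionnaire data into those models. Selection acted on a different quantity, the modified Claus or TC V6 given risk, and the Part 1 inclusion list has no risk-category criterion. On that reading the average row is not empty by design. This stands, and step 6 shows rejection anywhere from below nominal to 97%. It does not settle the matter, because the abstract and the second primary objective point to given risk.

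A reader might infer that selection makes the null false whatever density and SNPs do, so that rejection is certain. The documents do not support that. Selection breaks symmetry only in combination with movement; with no reclassification the test does not reject. Nor does a simulation that multiplies entry risk by a mean-1 lognormal factor (SD of log 0.2-0.5) prove it. Such a model rejects in 93.5-100% of runs with no selection at all, because the factor widens the spread and has a median below 1 (exp(−0.5²/2) = 0.88 at SD 0.5). Net downward movement is not guaranteed either, since V8 is expected to push risks up.

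It is also fair that up and down counts are already planned, so balanced movement would be visible in the table. Runs with and without the new factors are planned in item iii, and item ii regresses change in score on SNP313 and density. But those concern scores. No planned category table isolates the new factors at one date, and no confidence intervals are specified.

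**Conclusion.** The concern holds with limits. On either reading of the entry category, the test measures net direction between two time points and does not address the first primary objective. If given risk supplies the entry category, a significant result is close to uninformative: 8 women in 954 can produce it, and it appears in 94-100% of simulated studies with no systematic change at correlations of 0.6-0.9. If the entry category is recalculated, the distortion may be negligible or severe, and the documents do not allow a choice between the two.

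These rates rest on assumed SDs and correlations, equal distributions at both readings, n = 954 and alpha 0.05. The documents support neither certain rejection nor a wholly uninformative table. They do support saying that the p-value should not carry the conclusion.

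**What to change.** 1. State which entry category is used: the risk given at the time, or risk recalculated as at entry and with which model.
2. For the first primary objective, cross-tabulate NICE category from classical factors alone against classical factors plus density plus SNPs, with the same model at the same date.
3. For that table and for entry versus follow-up, report moves by starting category (for example moderate to average, moderate to high, high to moderate, high to average), each with a percentage and 95% CI.
4. Keep the Bowker test, if at all, as a descriptive test of net direction.
5. Note that selection on given risk can by itself produce net downward movement. This applies to the same-date table too if the classical-only estimate lies closer to the given risk than the full model does.

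The cost is SAP wording and a few tables from model runs already planned. One p-value loses its confirmatory role.

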## 2.0 AIMS & OBJECTIVES OF THE STUDY

### 2.1 Aims

The aims of this study are:

- i) To determine change in NICE categories of risk (average, moderate and high risk) when new risk factors are added to standard breast cancer risk models.
- ii) To explore how much new risk models (including MD, SNP313 and mutation testing) change risk estimates previously communicated to women as part of their management plan at first attendance at the FHRPC.
- iii) To explore the experiences of risk estimate changing over time in women with a family history of breast cancer. This will be assessed by using the re-evaluated risk estimates using the TC v8 and BOADICEA (with added MD, SNP313 and mutation testing) in a sub-sample of FH-Risk study participants and conducting qualitative interviews with women who choose to receive their re-evaluated breast cancer risk estimate.
- iv) To determine whether change in management differs between the three density measures in the Tyrer-Cuzick model. (BIRADS, Predictive VAS AND Volpara).
- v) To compare the degree of management change between the Tyrer-Cuzick (v8) and the BOADICEA model (v5) (Can-Risk).
- vi) To create information materials informed by participant interviews to communicate and inform women of their breast cancer risk re-evaluation and have these materials appraised by a sample of the FH-Risk women who have received their recalculated risk.

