- iv) **Comparison of mammographic density methods and the relationship with TCv8 risk scores** – scatterplots, intraclass correlation coefficients and Bland-Altman plots will be used to look at the relationship between different mammographic density methods. Risk scores will also be compared for TCv8 using different methods for measuring mammographic density to determine the impact this has on overall risk score. Changes in NICE risk categories will be compared using the different methods using the McNemar-Bowker test and differences in the continuous risk measures will be compared using repeated measures analysis of variance (ANOVA).

- v) **Reader reproducibility for BIRADS** - reproducibility for readers assessing BIRADS score will be determined using inter-reader and intra-reader statistics, using the McNemar-Bowker test to assess agreement within and between readers.

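### Across the three density measures, TCv8 risk is tested only for systematic shift (equal means, symmetry); no within-woman agreement is planned for the risk scores or NICE categories

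*Combined protocol and SAP*

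**What the plan says.** Section 2.1, aim iv, is: "To determine whether change in management differs between the three density measures in the Tyrer-Cuzick model". The measures are BI-RADS, Volpara and Predictive VAS. Under Table 1, management follows a woman's NICE category, with lifetime cut-offs at 17% and 30%.

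In Section 3.1, Statistical Analysis Plan, 3. Analysis, item iv plans three comparisons:

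- Density readings: scatterplots, and "intraclass correlation coefficients and Bland-Altman plots will be used to look at the relationship between different mammographic density methods".
- NICE categories: "Changes in NICE risk categories will be compared using the different methods using the McNemar-Bowker test".
- Continuous risk: "differences in the continuous risk measures will be compared using repeated measures analysis of variance (ANOVA".

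The stated purpose of comparing the scores is "to determine the impact this has on overall risk score". Item iv gives no acceptable difference and no decision rule, and it is labelled a secondary analysis.

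Two neighbouring items go further. Item iii compares TCv8 with BOADICEA on the risk scale and has "Bland-Altman plots used to show the agreement between the models". Item i reports the number and percentage of women who move category by "creating cross tabulations of risk categories at entry and at last follow-up". Item iv repeats neither for the density measures.

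**The concern.** Aim iv is a question about individual women: would the same woman be managed differently if another density measure were used? That calls for within-woman agreement in risk and in NICE category.

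The two tests on TCv8 output answer a different question. The ANOVA null is that mean risk is equal across measures. Disagreements in opposite directions cancel in the means and go into the error term, so for a given offset more disagreement makes significance less likely. McNemar-Bowker tests whether off-diagonal cells are symmetric, and any amount of balanced up-and-down movement satisfies it.

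The agreement statistics on the density readings do not fill the gap. BI-RADS has four points, Volpara reports percentage volume and VAS runs from 0 to 100. Volpara also outputs a grade mapped to BI-RADS categories, but the scale shared by all three is the TCv8 risk, where no agreement statistic is named.

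At stake is the answer to aim iv. A non-significant result does not show that the measures are interchangeable, and a significant one may reflect a trivial offset. The plan leaves room for this misreading, because item v uses the same symmetry test to assess agreement between BI-RADS readers.

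**Working it through.** The plan states no sample size, power or agreement limit for item iv, so there is no figure to reproduce. The behaviour of the two tests was examined by simulation.

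**Inputs from the documents.** Cut-offs are 17% and 30% (Table 1). The maximum n is 954 (Section 3.1, Risk recalculation), with the roughly 271 women still in follow-up as a low case. The odds ratio is 4 for the top v bottom density quintile (Section 1.2, Measurement of mammographic density).

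**Assumptions.** Lifetime risk is log-normal with median 25% and between-woman log-SD 0.40. The three measures have equal means and independent within-woman log-SD s. Tests are at 0.05.

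**Formulas.** ICC of log risk = 0.40² / (0.40² + s²). The 95% limits of agreement, as a ratio, are exp(±1.96 × s × √2). For s = 0.20: ICC = 0.16 / 0.20 = 0.80, and exp(±0.554) = 0.57 to 1.74.

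| s | ICC | Limits (ratio) | Pair discordant on NICE category | Any of three discordant |
|---|---|---|---|---|
| 0.05 | 0.98 | 0.87 to 1.15 | 9% | 13% |
| 0.10 | 0.94 | 0.76 to 1.32 | 17% | 25% |
| 0.20 | 0.80 | 0.57 to 1.74 | 32% | 48% |

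**Rejection rates.** In every row the ANOVA and a single pairwise McNemar-Bowker test each reject in about 3-6% of runs. At s = 0.20, n = 954 and 4,000 runs, the ANOVA rejects in 4.8% (log scale) or 5.2% (raw scale). One McNemar-Bowker test rejects in 3.7%, and at least one of the three pairwise tests in 10.7%. The pattern is similar at n = 271.

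**Opposite case.** With s = 0.05 and n = 954, an offset of 1-2% in one measure makes the ANOVA significant in over 99% of runs. At 2%, pairwise discordance is 8.7%, against about 9% with no offset, and at least one pairwise McNemar-Bowker test is significant in 91.5% of runs.

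**What spread is plausible?** The documents give no between-measure correlation ρ. As a rough scale, take the odds ratio of 4. Under normality the means of the top and bottom quintiles lie 2.80 SD apart, so the log odds ratio per SD is ln 4 / 2.80 = 0.495. If each measure carries that full weight, s = 0.495 × √(1 − ρ). The ranges below cover medians of 20-30% and between-woman log-SD of 0.30-0.50.

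- ρ = 0.9: s = 0.157, 21-29% discordant
- ρ = 0.8: s = 0.221, 29-39% discordant
- ρ = 0.7: s = 0.271, 34-45% discordant

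Over the same ranges, s = 0.10 gives 14-19% and s = 0.05 gives 7-10%.

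**The case against.** Comparing means is legitimate. A systematic shift between density measures is a real question, and repeated measures ANOVA is a standard test of it on paired scores. NICE categories are also compared, and the 3x3 table needed for McNemar-Bowker contains the discordant percentage. All of this stands. The gap is an omission from what is reported, in a secondary analysis with no decision rule.

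The simulation can also be challenged. The 3-6% rejection follows from setting the means equal; it is simply the level of the tests. With a 5% offset in one measure and method-specific log-SD of about 0.13 to 0.25, the ANOVA rejects in 98-100% of 1,500 runs. The two failures also belong to different settings: at that larger spread a 1% offset is significant in only 13-37% of runs. These points stand as well. They limit how often each failure would occur, but they leave intact that neither p-value tracks within-woman disagreement.

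A reader might infer that the ANOVA alone judges the effect of the density measure. The same sentence of item iv plans McNemar-Bowker, so the documents do not support that. A reader might also infer that women will drop out of the comparison, because Section 3.1 says that "the raw mammogram images required for processing MD were not retained". That remark explains why density was not fed back earlier. The documents give no count of missing images for this study, plan all three measures at both time points, and do not say how incomplete sets would be handled. No loss should be asserted.

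**Conclusion.** The concern holds as a gap in the analysis serving aim iv. For TCv8 risk, item iv plans a test of equal means and a test of symmetry, and no measure of within-woman agreement. Both can be non-significant with 9%, 17% or 32% of women in different NICE categories for a pair of measures (s = 0.05, 0.10 or 0.20). When measures agree closely, a 1-2% offset is significant with only about 9% discordant.

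These percentages depend on the assumed log-normal risk, its median and spread, and s; none is a figure from the plan. It is tempting to say that a quarter or more of women would be reclassified. With between-woman log-SD 0.40, that needs s of about 0.15-0.17 or more, and the documents do not establish such a spread. Nor do they say that a non-significant result will be read as interchangeability; the plan merely does not guard against it.

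**What to change.** Add to item iv, for each pair of density measures:

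- Bland-Altman limits of agreement for TCv8 10-year and lifetime risk, on the log scale if the scores are skewed. Item iii already does this for TCv8 v BOADICEA.
- A 3x3 NICE cross-tabulation with the percentage of women discordant and its 95% CI, named as the headline result for aim iv.

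Keep the ANOVA and McNemar-Bowker as tests of systematic shift only, and state that a non-significant result will not be taken as interchangeability. A linear mixed model could replace the ANOVA: it gives the mean offset with a CI and uses any women who lack one measure.

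Precision should be adequate. At 32% discordant the 95% half-width is 1.96 × √(0.32 × 0.68 / 954) = 3.0 percentage points, or 5.6 points with n = 271.

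The cost is a change of SAP wording and a few extra tables in a secondary analysis, from scores that will already have been computed.
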